10.3.2.3 Completing the VOIDING DIARY DATA ENTRY FORM

After reviewing the diary and totaling the episodes, fill in the VOIDING DIARY DATA ENTRY FORM. The Date of Visit is the day the participant returns with the completed diary. Enter the totals that you have calculated on the Voiding Diary. If the participant has filled in the diary completely and accurately, and if she has 10 or more episodes of incontinence recorded for a week, she is eligible to continue in the study. The diary will be considered complete and accurate if “All of the time”, or “Most of the time” is marked on *at least five diary days*. The reviewer should check to make sure that each episode marked has complete data.

- From the shaded boxes on the diary, enter the total daytime and nighttime episodes onto the data form. Check to make sure you included both pages for each day as well as any “Extra Entries” from the last page/s of the diary. Remember to add these entries into the totals for the date listed in the left-most column.
- Enter a zero in the corresponding boxes if the participant never answered “yes” to “**did you urinate in the toilet?**” and/or “**did you leak urine?**” on a given day.
- Fax the completed form to the data system at the Coordinating Center

10.3.3 Dipstick Urinalysis

Urinary tract infection may cause or worsen urinary incontinence. Therefore, participants who may have a urinary tract infection will be excluded. The dipstick urinalysis will be performed to detect possible urinary tract infection. A “clean catch” urine sample is required for the dipstick test.

Procedure:

- Give the participant a sanitary wipe and ask her to wipe the genital area to remove any bacteria prior to urinating
- Instruct the participant to start her urine flow into the toilet, stop the flow and then continue urinating into the urine container that has been provided. A participant instruction sheet is attached as Appendix 10A.
- About 1 ounce of urine is sufficient for the test
- Dip the reagent strip in the urine, remove, and compare each reagent area with the corresponding color chart on the bottle label at the elapsed time interval specified on the bottle.
- Participants with a normal result (negative) for leukocyte esterase and a normal (negative or trace) test for blood are eligible for the study.
- Complete the DIPSTICK URINALYSIS FORM.

Abnormal Results: The following abnormal results make the participant **ineligible** for PRIDE:

Leukocyte Esterase	Blood	Hemolyzed Blood
Trace	Moderate	Small (+)
Small (+)	Large	Moderate (++)
Moderate (++)		Large (+++)
Large (+++)		

Participants with any of the above results will be informed that they may have a urinary tract infection and/or blood in their urine and will be referred to a physician for follow-up. The screening procedures may continue as long as the participant is willing to have any problem treated, and to return for a repeat dipstick urinalysis. The dipstick test must be repeated even if blood is present due to menstruation.

10.3.3.1 Repeat Urine Dipstick

Treatment for a urine infection generally involves a week-long course of antibiotics. The test should be done at SV1 and repeated if necessary at SV2 after the participant has received effective treatment for a urinary tract infection. The dipstick urinalysis performed at a Urodynamic Study visit can serve as a repeat test if necessary. **The results of a repeat test should be recorded on a new data form with the appropriate visit bubble filled in.**

A participant who has an abnormal urine dipstick result for any reason may be rescreened *once* for eligibility.

If the participant does not return for a repeat urinalysis or if the repeat urinalysis is still positive, the participant is not eligible for PRIDE. Complete a second DIPSTICK URINALYSIS FORM, as necessary, and the Inclusion/Exclusion Checklist if appropriate, marking "Yes" for item D of Exclusion Criteria.

10.3.4 Vital Signs

Measure the participant's blood pressure and pulse using the Dinamap Monitor Pro 100 according to the instructions in Chapter 14.2. Enter the results on the VITAL SIGNS data form.

Uncontrolled hypertension is an exclusion criterion in PRIDE. Blood pressure must be less than 160/100 mmHg, with or without an anti-hypertensive medication, in order for the participant to qualify for the trial. For added safety, if the blood pressure is higher than 140/90 at SV1 the participant should be referred to her health care provider for appropriate treatment. In this case, measure the blood pressure again at SV2 for safety purposes and to confirm that the participant has consulted her physician. **When a repeat BP measurement is made at SV2 a new VITAL SIGNS form must be completed.** Blood pressure must be less than 160/100 at either SV1 or SV2 in order for the participant to meet entry criteria.

If the participant has uncontrolled hypertension (BP equal to or greater than 160/100 at SV1 and SV2) she is not eligible for PRIDE. In this case cancel the remainder of the visit and update the Inclusion/Exclusion checklist, marking

“Yes” for Exclusion Criteria, item H.

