6.3 Exclusion Criteria

1. current use, or use within the previous month*, of medical therapy for incontinence or weight loss
2. pregnant or gave birth in the previous 6 months
3. urinary tract infection (dipstick urinalysis positive for leukocyte esterase, nitrites or blood) or report having ≥ 4 urinary tract infections in the preceding year
4. incontinence of neurologic or functional origin (by history)
5. report prior anti-incontinence or urethral surgery, pelvic cancer or pelvic irradiation
6. report significant medical conditions of the genitourinary tract (genitourinary fistula, interstitial cystitis, symptomatic pelvic organ prolapse)
7. report a medical condition that would affect the safety and/or efficacy of a weight management program involving diet and physical activity, including type 2 diabetes requiring medical therapy that may cause hypoglycemia, chronic steroid use or uncontrolled hypertension (systolic blood pressure >180 mm Hg or diastolic blood pressure > 100 mm Hg); women with a history of coronary heart disease may participate with written approval from their primary care physician
8. engaged in an active weight loss program and/or experienced a weight reduction of 10 lbs or more in the past 3 months
9. report conditions that, in the judgment of the clinical center Principal Investigator, render potential participants unlikely to follow the protocol for 18 months, including illness likely to be terminal within 2 years, plans to move, substance abuse, significant psychiatric problems, or dementia
10. participating in another research study that involves investigational drugs or can potentially confound the results of PRIDE

* Potential participants may be re-screened one month after stopping medical therapy for incontinence or obesity. Prior medical therapy for incontinence or obesity will not affect eligibility but participants will be asked not to initiate any

treatment for incontinence or obesity during the study period except as directed by the study protocol.

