In this case, mark the Inclusion/Exclusion form as follows: If the participant responds “Yes” to 16a, 16b, 16c, or 16d, then mark “Yes” for Exclusion Criteria, item G. If the participant responds “Yes” to 16e, 16f or 16g, then mark “Yes” for Exclusion Criteria, item E. If the participant marks “don’t know” to any of the questions 16a to 16g she is still eligible to continue screening.

Questions 17. This question probes for a history of hypertension. A “yes” response does not exclude the participant. Blood pressure will be measured during screening to determine eligibility.

Question 18. High cholesterol does not exclude the participant.

Question 19. If the participant has a history of coronary heart disease she is not excluded from PRIDE, but she must obtain approval from her health care provider in order to participate in PRIDE. Please confirm that she has obtained a letter and make sure the letter is filed in her study binder prior to the Randomization Visit.

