APPENDIX 10C HEALTH HISTORY

Participant ID #	Acrostic	Date of Visit	Staff ID #
 13658 		 /  /  <small>Month Day Year</small>	

HEALTH HISTORY
(Self-Administered)

Visit: Screening

16. Has a doctor ever told you that you had, or currently have, any of the following conditions or diseases?
- a. A fistula or a hole in your bladder, rectum or near there?
- Yes → **NOT ELIGIBLE**
 No
 Don't Know
- b. A birth defect leading to urine leakage?
- Yes → **NOT ELIGIBLE**
 No
 Don't Know
- c. Urine leakage starting in childhood?
- Yes → **NOT ELIGIBLE**
 No
 Don't Know
- d. Interstitial cystitis or very painful bladder?
- Yes → **NOT ELIGIBLE**
 No
 Don't Know
- e. Problems with your spinal cord or back leading to urine leakage?
- Yes → **NOT ELIGIBLE**
 No
 Don't Know

Participant ID #	Acrostic	Date of Visit			Staff ID #
    	    	 /  /   	  	  	  
		Month	Day	Year	

HEALTH HISTORY (Self-Administered)

Visit: Screening

16. (Continued)
Has a doctor ever told you that you had, or currently have, any of the following conditions or diseases?
- f. Multiple sclerosis?
- Yes → **NOT ELIGIBLE**
- No
- Don't Know
- g. Parkinson's disease?
- Yes → **NOT ELIGIBLE**
- No
- Don't Know
17. Has a health care provider ever told you that you had, or currently have, hypertension?
- Yes → If BP is $\geq 160/100$ at RV, participant is **NOT ELIGIBLE**
- No
18. Has a health care provider ever told you that you had, or currently have, high cholesterol?
- Yes → Requires MD approval
- No
19. Has a health care provider ever told you that you had, or currently have, coronary heart disease?
- Yes
- No

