12.2 PREPARATION FOR THE VISIT

This is the last occasion prior to randomization to confirm the participant's eligibility for PRIDE. The participant can be randomized at any point during the visit as long as all inclusion/exclusion criteria have been met.

Forms/Procedures Needed for Randomization Visit

Review 2 nd 7-Day Voiding Diary
Weight and Abdominal Circumference
UI Symptoms
Collect/Weigh 24-Hour Pads
Randomization/Inclusion/Exclusion Checklist
Randomization Envelopes
Staying Dry Handbook

Please have a calculator available.

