14.2 VITAL SIGNS: BLOOD PRESSURE AND PULSE

14.2.1 Schedule of Administration

Seated blood pressure and heart rate measurement is performed during screening, at the Randomization Visit and at months 6, 12 and 18.

It is suggested that seated blood pressure and heart rate measurements be done at the beginning of a visit, after the participant has been sitting quietly for at least five minutes to allow blood pressure and heart rate to stabilize after movement or activity, such as walking.

During this five minute resting period, participants should NOT be engaging in any of the following: Reading, filling out forms, talking or crossing their legs.

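### Operations Manual 10.3.4 orders a repeat blood pressure at SV2 for safety, but once SV1 was below 160/100 no SV2 value can trigger its exclusion, and the later checks are partial and inconsistent

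*Protocol*

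**What the plan says.** Section 10.3.4 of the Operations Manual sets a qualifying limit of less than 160/100 mmHg, treated or untreated. A woman above 140/90 at SV1 is referred to her provider, and staff must "measure the blood pressure again at SV2 for safety purposes and to confirm that the participant has consulted her physician", using a new Vital Signs form. The entry rule follows: "Blood pressure must be less than 160/100 at either SV1 or SV2 in order for the participant to meet entry criteria." Staff mark exclusion item H when pressure is uncontrolled, defined as "BP equal to or greater than 160/100 at SV1 and SV2".

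Protocol section 6.3, item 7, excludes "uncontrolled hypertension (systolic blood pressure >180 mm Hg or diastolic blood pressure > 100 mm Hg". It names no visit and no number of readings. Protocol section 8.3.2 allows a repeat at SV2 when the criterion was failed at SV1.

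Four other places bear on what happens later:

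- Section 14.2.1: "Seated blood pressure and heart rate measurement is performed during screening, at the Randomization Visit and at months 6, 12 and 18."
- Appendix 10C, question 17: for a woman who answers Yes to a history of hypertension, a reading of 160/100 or more "at RV, participant is" not eligible.
- Section 10.3.6.1, on the same question: "Blood pressure will be measured during screening to determine eligibility."
- Section 12.2: the list headed "Forms/Procedures Needed for Randomization Visit" does not include vital signs.

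**The concern.** The manual singles out women with raised pressure at SV1, sends them for treatment and measures them again. It then gives the second measurement no power to change their status if the first was under 160/100. The reading is ordered for safety, yet for these women it can only confirm entry.

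Uncontrolled hypertension is a safety exclusion for a diet and exercise programme. A site following 10.3.4 to the letter and a site applying 6.3(7) to the most recent value could decide differently about the same woman. Whether an RV reading settles the matter depends on which part of the manual the site consults.

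**Working it through.** There is no planned figure to reproduce; the point is one of logic.

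**1. The two rules over the possible outcomes** (pass means below 160/100):

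| SV1 | SV2 | Under 10.3.4 | If a failing SV2 defers |
|---|---|---|---|
| pass | pass | meets entry | meets entry |
| pass | fail | meets entry | deferred |
| fail | pass | meets entry | meets entry |
| fail | fail | excluded | excluded |

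Section 10.3.4 excludes 1 of the 4 outcomes and neither of the 2 that follow a passing SV1.

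**2. Enumeration.** Take systolic 130 to 200 and diastolic 80 to 120 in steps of 5, which gives 15 × 9 = 135 values per visit. Passing SV1 values number 6 × 4 = 24. Of these, 3 × 3 = 9 do not exceed 140/90, leaving 15 that pass and still require a repeat. That gives 15 × 135 = 2,025 SV1/SV2 pairs.

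- Excluded by 10.3.4: 0, whether failing 160/100 means either component or both.
- SV2 meeting 6.3(7) while 10.3.4 admits: 15 × (4 × 15) = 900 with diastolic above 100, plus 15 × (4 × 5) = 300 with systolic above 180 and diastolic at or below 100. The total is 1,200.

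These counts show the logic and are not prevalences. An SV2 systolic of 160 to 180 with diastolic at or below 100 breaches only the manual's limit unless diastolic is exactly 100, which also fails the manual alone.

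**3. How often.** The documents give no blood pressure distribution, so the following is illustration on assumed values. Let U be usual diastolic, with independent visit-to-visit variation of SD 6 (range 5 to 8), and let t be the fall after referral. The chance of a diastolic of 91–99 at SV1 and 101 or more at SV2 is

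[Φ((99.5 − U)/SD) − Φ((90.5 − U)/SD)] × [1 − Φ((100.5 − U + t)/SD)].

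For U = 95, SD 6, t = 0: [Φ(0.75) − Φ(−0.75)] × [1 − Φ(0.917)] = 0.547 × 0.180 = 0.098.

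| Usual diastolic | t = 0 | t = 5 |
|---|---|---|
| 85 | 0.1% (0.0–0.6) | 0.0% (0.0–0.1) |
| 90 | 1.6% (0.8–3.4) | 0.2% (0.0–0.9) |
| 95 | 9.8% (8.6–10.5) | 2.2% (1.1–4.0) |
| 100 | 19% (17–20) | 7.4% (5.9–8.8) |

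Repeats triggered only by systolic pressure are not counted.

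**4. Later checks, side by side.** Section 14.2.1 schedules an RV reading. The table in Protocol section 8.1 shows none, the RV list in 12.2 omits vital signs, and the visit map in Appendix 4A marks them Y rather than the mandatory X. Appendix 10C makes an RV value decisive, but only for women who report hypertension; 10.3.6.1 says screening readings decide. Section 12.3.6 has staff review every criterion before randomizing, and item H in Appendix 12A lists Vital Signs among its source forms. Item H states no limit and no visit, however, and the instruction on when to mark it for blood pressure is the both-visits rule in 10.3.4. The recheck list in Appendix 9B, used when RV falls more than 3 months after SV1, has no blood pressure item.

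**The case against.** The strongest reply is that 6.3(7) specifies neither visit nor number of readings, so 10.3.4 may legitimately define uncontrolled hypertension as elevation at both visits. With one reading recorded per visit (14.2.2), that guards against excluding a woman on a single noisy value. The protocol itself does not schedule an SV2 reading after an SV1 pass. The repeat also serves to confirm that she saw her physician, and the main safety action, referral above 140/90, occurs well below either limit.

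Much of this stands. A reader might infer that 10.3.4 flatly contradicts 6.3(7); the documents do not support that, because the conflict appears only when 6.3(7) is applied to the latest reading. A reader might also infer that the repeat is pointless, or that a woman at 150/105 passes unchecked to randomization. Neither follows: the repeat has a second purpose, and the SV2 form is available for the item H review.

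What the reply does not answer is that 8.3.2 supports the repeat as a rescue after failure, not as a reading that a previous pass overrides, and that the later checks do not give sites one consistent rule.

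**Conclusion.** The point holds in a limited form. Within 10.3.4, no SV2 value can exclude a woman who passed SV1; this follows from the text without assumption. That she then meets a protocol exclusion requires applying 6.3(7) to the latest reading, and an SV2 diastolic above 100 or systolic above 180. That is the natural way to read a safety criterion, but it is an inference.

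The number of women cannot be estimated and is probably small: on the assumed values the diastolic conflict is rare unless usual diastolic lies close to the limit. Blood pressure is not an outcome (14.2.2), so the concern is safety and uniform eligibility between sites, not the treatment comparison. It merits correction because the change is cheap and uses readings the manual already schedules.

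**What to change.** In 10.3.4, replace the entry and exclusion sentences with a rule of this kind: a reading below 160/100 at SV2 rescues a failed SV1; failure at both visits excludes; a failing SV2 after a passing SV1 defers randomization until a further reading, normally the RV reading in 14.2.1, is below 160/100. Deferral is preferable to refusal on one value.

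Add Vital Signs to the RV list in 12.2, and make the RV rule in Appendix 10C apply to every deferred woman, whether or not she reports hypertension. The sentence on question 17 in 10.3.6.1 should then acknowledge the RV reading for these women.

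The cost is a few lines of manual text and one Vital Signs form at RV. A few women will be deferred or refused, including some with an SV2 systolic of 160 to 180 who meet the protocol's limit but not the manual's.

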10.3.5 Height /Weight

Measure the participant’s height and weight according to the directions in Chapter 14.1, Physical Measurements. Record the results on the HEIGHT/WEIGHT data form.

Calculate the Body Mass Index by dividing the weight in kilograms by the square of the height in meters. Round to the nearest whole number and record the result in BMI, item #1. To confirm the calculation, look up the BMI on the chart (Appendix 10B). The two numbers should be very close. (The chart is less precise than the calculation). If they are not, please recheck your measurement and calculations and make any necessary corrections to the data form. The calculated value is the value that determines eligibility.

If the BMI is **less than 25kg/m²** or **greater than 50kg/m²** the participant is not eligible. In this case please fill out the Inclusion/Exclusion form, marking “No” for Inclusion criteria, item B.

10.3.6 Health History

The health history is a self-administered questionnaire that should be filled out by the participant during the clinic visit and checked by study staff before the participant leaves the clinic. Review the form for missing responses, for completion of sub-category questions (e.g. if #2 is answered “yes” then 2a should be completed) and for information that affects eligibility. **There are some important exclusion criteria contained in the health history.** An interviewer-annotated version of this form that highlights the eligibility questions is attached as Appendix 10C.

10.3.6.1 Health History Questions

Questions 1 – 4. These are demographic questions only and have no bearing on eligibility. Check for completeness.

Please note that the following questions 5 – 9 do not exclude the participant:

Question 5. Peripheral vascular disease or surgery for PVD does not

exclude the participant.

Question 6. A stroke, cerebral infarction, cerebrovascular accident (CVA) or a transient ischemic attack (TIA) do not exclude the participant, however, the sequelae of these conditions may. The participant is ineligible for the study if she is unable to walk without the use of a cane or walker, or if she cannot read or write well enough to complete the questionnaires and diaries.

Question 9a and 9b. Hysterectomy and removal of the ovaries do not exclude women from PRIDE.

Question 9c. Surgery for prolapse of the bladder, uterus, vagina or rectum does not exclude the participant. A urethral dilation done to relieve pain from repetitive urinary tract infections (cystitis) does not exclude the participant.

Question 10. If the participant has trouble remembering when she started leaking urine continually, help her recall by asking her to think of other significant events or dates that may have occurred around the same time. Alternatively, as a recall prompt, ask her if she was leaking urine when she was 30 or 35 or 40 years of age, etc. Note that, in order to qualify for the study, she should have been leaking urine for 3 months or more at the time of the Eligibility Screening. Please confirm with her that she has been leaking urine for at least 3 months.

Questions 11 – 12. These questions do not affect eligibility. Please check to make sure there is a response for each question.

Question 13. If the “Yes” bubble is marked then either “Yes” or “No” in the side-box must be marked. If the “No” bubble is marked, one or more of the bubbles in the next side-box must be marked. This question does not affect eligibility.

Question 14. This question relates to the economic impact of incontinence and does not affect eligibility. If the response to question 14 is “Yes”, questions 14a and 14b must be answered.

Question 15. One or more bubbles must be marked. None of these conditions excludes the participant.

Question 16a - 16g. These questions pertain to physical or neurological problems that may affect incontinence. A **“Yes” response to any one of these questions excludes the participant.**

In this case, mark the Inclusion/Exclusion form as follows: If the participant responds “Yes” to 16a, 16b, 16c, or 16d, then mark “Yes” for Exclusion Criteria, item G. If the participant responds “Yes” to 16e, 16f or 16g, then mark “Yes” for Exclusion Criteria, item E. If the participant marks “don’t know” to any of the questions 16a to 16g she is still eligible to continue screening.

Questions 17. This question probes for a history of hypertension. A “yes” response does not exclude the participant. Blood pressure will be measured during screening to determine eligibility.

Question 18. High cholesterol does not exclude the participant.

Question 19. If the participant has a history of coronary heart disease she is not excluded from PRIDE, but she must obtain approval from her health care provider in order to participate in PRIDE. Please confirm that she has obtained a letter and make sure the letter is filed in her study binder prior to the Randomization Visit.

10.3.7 The 7-Day Diet and Exercise Diary

Self-monitoring is a cornerstone of the behavioral intervention and will be encouraged throughout the study in the weight loss group. Participants will be asked to self-monitor dietary intake (foods eaten, portion size, calorie content, and fat grams) and physical activity (including type, duration, and number of steps walked, when applicable) in a seven-day diary that will be provided to them. The ability and willingness to self-monitor is an entry criterion for PRIDE.

At SV1, give the Run-in Food and Exercise Diary to the participant and ask her to record her food and beverage intake and type of exercise each day for 7 days. The number of calories, fat grams and steps taken is *not required* during screening. The diary should be kept for 7 consecutive days. Ask the participant to bring the completed diary with her to her Screening Visit 2.

